### 11.2 Sample Size

Up to 39 patients may be included in the dose escalation phase. This number is based on the operational characteristics in [Appendix 1](#), including the up to 10 additional patients who may be added to any dose-level as described in section [6.2.1.4](#).

The impact of sample size on the detectability of AEs during dose escalation (when N=3, 6, or 9 patients at a dose level) and during dose expansion (when N=30) is shown in [Table 11-1](#).

**Table 11-1 Probabilities of observing adverse events**

Probability of an event	Probability of making at least 1 observation of an event in N patients			
	N=3	N=6	N=9	N=30
30%	66%	88%	96%	100%
10%	27%	47%	61%	96%
5%	14%	26%	37%	79%
2%	6%	11%	17%	45%
1%	3%	6%	9%	26%
0.1%	0%	1%	1%	3%

### 11.3 Analysis Populations of Interest

#### 11.3.1 Full Analysis Set

The full analysis set (FAS) will include all patients enrolled in the trial who received at least 1 dose of nivatrotamab. Patients who do not fulfil relevant inclusion criteria (e.g., no baseline measurable disease) but still receive the study drug, may be excluded from the FAS.

#### 11.3.2 Safety Analysis Set

The safety analysis set (SAF) will include all enrolled patients who receive at least 1 dose of nivatrotamab.

Unless stated otherwise, the SAF will be used for the analyses related to the primary objective.

#### 11.3.3 DLT Evaluatable Analysis Set

The DLT evaluable analysis set (DAS) is a subset of the SAF. This analysis population will include patients in the dose escalation phase who receive at least 80% of the planned doses on each of the 4 administrations in the DLT evaluation period and who had sufficient safety evaluations, or who had a DLT during the DLT evaluation period.

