16. Impending need for palliative radiotherapy or surgery for pathological fractures and/or for medullary compression up to 3 weeks prior to the first planned dosing of the IMP per protocol (palliative radiation for other reasons within 2 weeks)
17. History of other active malignancy within the past 3 years prior to the first planned dosing of the IMP per protocol (excluding non-melanoma skin cancers, carcinoma in situ of the cervix, ductal carcinoma in situ of the breast, incidental prostate cancer (T1a, Gleason score ≤ 6, prostate specific antigen (PSA) less than 0.5 ng/ml)
18. Patients with a significant intercurrent illness (any ongoing serious medical problem unrelated to cancer or its treatment) that is not covered by the detailed exclusion criteria and that is expected to

Determination of MTD and RP2D: The mBOIN-based MTD will be preliminarily estimated statistically as the dose level with the observed DLT rate closest to the target toxicity level (i.e., 28%). After the mBOIN dose -escalation algorithm has been completed, the DMC and the Sponsor will determine the MTD and the RP2D. The selection of the RP2D will balance the frequency and severity of AEs with any observed dose response for clinical activity. It will be based on a review of the available safety information, including AEs and safety laboratory values, relevant PK data, and observations made after the end of the DLT evaluation period. The RP2D may not exceed the MTD.
 
For the purpose of dose escalation, DLTs will be collected and assessed throughout Cycles 1 and 2, covering a treatment period of 4 weeks. This will allow for the evaluation of up to 3 IMP administrations.
 
Phase 2 (dose expansion): In phase 2, the RP2D will be used to further assess safety and tolerability, as well as the clinical activity of nivatrotamab.
	
Number of patients (planned)	Up to 39 patients are planned to be dosed in phase 1 (dose escalation) and 30 additional patients in phase 2 (dose expansion). No more than 69 patients in total will be dosed in the trial.
Investigational Medicinal Product (IMP)	For this trial, the Sponsor, Y-mAbs, will provide nivatrotamab, 2 mg/mL. No other medicinal products or auxiliary medicinal products will be provided by Y-mAbs. The IMP, nivatrotamab, will be administered SC according to the treatment schedule.

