b: Cycles 2 (inpatient Days 1 and 2) and 3 only, unless patient is hospitalized due to cytokine release syndrome (CRS)

c: Cycle 2 only

d: All patients to be followed up for safety reporting for 30 days after the last investigational medicinal product (IMP) dosing. Thereafter, long-term safety will be recorded by registration of related SAEs up to 12 months after the last dose. Vital status and disease progression for follow up on progression-free survival (PFS) and overall survival (OS) will be up to 12 months after the last dose. The Investigator should collect CT scan reports for tumor assessments every 8 weeks or according to the local standard of care. The FU assessments can be done locally at the referral site.

e: This will only include anti-cancer therapy.

f: Physical examination at screening and the EOT visit should include a neurological examination.

g: Every second cycle (e.g., Cycle 2, 4, 6, 8, 10, and 12)

h: For baseline. In addition, an MRI must be performed if a patient develops a central nervous system (CNS) AE ≥ grade 2.

i: Echocardiogram/MUGA to be performed on Day 11 of treatment cycle 1, and Day 4 of cycle 2. Assessment must be analyzed and reviewed by Investigator prior to dosing in cycle 2 and cycle 3

j: Mandatory 48 hours hospitalization in Cycles 1 and 2; optional thereafter (pending clinical signs of possible CRS).

From Cycle 3 onward, the minimum patient monitoring time following dosing will be 6 h; the patient may be observed for this duration as an outpatient or be hospitalized depending on AEs and Investigator's judgement.

k: All AEs (including SAE, and AESIs) should be reported from the signing of the informed consent until 30 days after the patient's last dose of IMP. Thereafter and during the follow-up period, only SAEs considered related to IMP, study procedures and secondary malignancies (regardless of causality) should be reported. DLTs should be reported from the first dose of IMP and the following 28 days.

l: CRS grading and ICE score should be performed predose on dosing days and once per day when the patient is attending the ward for the first 3 cycles, thereafter only if clinically indicated. If the ICE score decreases from baseline, neurotoxicity should be assessed with the use of the ICANS grading system (see section 7.2.4).

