m: CT scan of the neck, chest, and abdomen at screening and Week 4, 8, 16, and 24, with an assessment window of  $\pm 4$  days. Confirmatory scanning for patients who have obtained PR or CR will be undertaken approximately 4 weeks after the initial response.

n: Only if more than 6 weeks since last CT scan

o: Assessment of response by the Primary Investigator (progression and survival).

p: Pre-dose on Day 1 and 8 of Cycle 1, Day 1 of Cycles 2-13, and EOT.

q: Vital signs to be monitored and registered every 2 hours on Day 1 and Day 2 of cycle 1 and cycle 2 during daytime and every 4 h during nighttime.

r: Cycle 1 day 1 the IL-6 sample must be taken pre-dose (baseline), all other IL-6 samples should be taken the day after IMP administration (dosing day +1) and should be taken at the same time of the day ( $\pm 60$  min)

s: ECG performed pre-dose on dosing days.

Table 3-2 Schedule of time and events: phase 2 (dose expansion)

Treatment / Measurements / Evaluations	SCR	Cycle 1 (D1 to 14); 1 cycle = 14 days a DLT evaluation period = 2 cycles								Cycle 2 to 13				EOT ±4d	Follow up d
		<21 days	■	■	■	■	■	■	■	■	■	■	■		
Informed consent	X														
Eligibility check	X														
Demographics and baseline characteristics	X														
Medical history, concomitant illness	X														
Concomitant medication	X	X	X	X	X	X	X	X	X	X	X	X	X	X e	
Physical examination	X f	X	X			X	X			X				X f	
Height	X														
Weight	X	X				X			X	X				X	
ECOG score	X	X								X				X	X
Vitals signs	X	X g	X g	X	X	X g	X g	X	X	X g	X g	X	X	X	
HCG in FOCP (urine or blood)	X										X g				X
Urinalysis (dipstick)	X	X				X				X					X
Cranial and Spinal MRI h	X														
ECG	X	X s	X			X s	X			X s	X				
Echocardiogram/MUGA	X								X i					X i	
Hospitalization j		X	X			X	X			X	X				
Premedication		X	X			X	X			X	X				
███████████		■													
███████████						X				X					
PK, see Table 8-1		X	X							X					
AE (CTCAE version 5)	X k	X	X	X	X	X	X	X	X	X	X	X	X	X	X
CRS grading l		X	X	X	X	X	X	X	X	X	X	X	X	X	
ICE score l		X	X	X	X	X	X	X	X	X	X	X	X	X	
Hematology	X	X	X	X	X	X	X	X	X	X	X	X	X	X	
Clinical chemistries	X	X	X	X	X	X	X	X	X	X	X	X	X	X	
Coagulation	X	X	X	X	X	X	X	X	X	X	X	X	X	X	

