### 6.2.1.3 Dose Escalation Stages

The dose escalation phase will consist of 2 stages: the initial accelerated titration stage followed by a standard titration stage (Figure 6-1).

In the accelerated titration stage, patients will be recruited and treated in single-patient cohorts. These single-patient cohorts may optionally be expanded with up to 2 additional patients for the purpose of obtaining additional PK and/or pharmacodynamic data.

The initial accelerated titration stage will end, and the single-patient cohort mandatorily expanded with (at least) 2 additional patients once either:

- Dose level 3 is reached, or
- During the DLT evaluation period (28 days), a patient is observed with:
  - any grade  $\geq 2$  AE (excluding toxicities clearly related to disease progression or intercurrent illness), or
  - a protocol defined DLT (section 6.2.3).

whichever occurs first

This will mark the end of the accelerated titration stage and the beginning of the standard titration stage. Hereafter, patients will be allocated to dose-levels typically in cohorts of 3. As the mBOIN design allows cohort-sizes to vary, the actual cohort sizes may differ from 3.

In the standard titration stage, cohorts will be allowed to include only 2 patients who are evaluable for DLT, provided that none of the 2 patients have experienced any related, grade  $\geq 3$  AE during the DLT evaluation period.

If patients are withdrawn prematurely without having experienced a DLT, they will be considered non-evaluable and may be replaced.

In cohorts that include more than 1 patient in the dose escalation part, there will be sequential enrolment. At a particular dose level, there must be at least 3 days between the first dose of the first patient and the first dose of the subsequent patients in the same cohort.

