### **List of exceptions: non-hematological exceptions**

The following AEs will not constitute DLTs (however, they should be reported as AEs/SAEs according to the reporting guidelines).

- Grade 3 laboratory values considered not clinically significant
- Grade 3 headache, nausea, diarrhea, and vomiting, persisting for  $< 48$  h (with adequate supportive care)
- Grade 3 elevations of ALT/AST  $\leq 8 \times$  ULN or baseline ALT/ AST (in case baseline above ULN at study entry) improved to  $<$  grade 3 within 14 days
- Grade 3 hypertension lasting  $< 48$  h
- Grade 3 Fever lasting  $< 72$  h
- Grade 3 Fatigue lasting  $< 7$  days

AEs that are self-limited and resolve within a short time frame will not constitute DLTs; however, they should be reported as AEs/SAEs according to the reporting guidelines.

For the purpose of dose escalation, DLTs will be collected and assessed throughout Cycles 1 and 2, covering a treatment period of 4 weeks. This will allow for the evaluation of up to 3 investigational medicinal product (IMP) administrations.

DLTs must be entered in the clinical AE report form and reported from the site to the Sponsor within 24 h of the Investigator's first knowledge of the event. In case any of the side effects mentioned in the DLT definitions occur during Cycles 2 to 5 in Phase 1, these will be discussed at the first upcoming preplanned DMC meeting, and the Sponsor's safety committee will evaluate the DMC recommendations for further dosing.

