#### **9.9.3 Data Monitoring Committee**

An external DMC will be established to assure patient safety and will function independently of all other individuals associated with the conduct of the trial, including the site Investigators participating in the trial. The DMC will consist of a minimum of 2 physicians whose expertise covers relevant specialties.

During the conduct of phase 1 of the trial, after completion of the DLT evaluation period (2 treatment cycles/28 days) for the last patient in each dose level, the DMC will evaluate the available safety information and recommend trial continuation or termination. If continuation is recommended, the DMC will recommend to the Sponsor whether the dose should be escalated, de-escalated, or held at the same dose level.

During phase 1 and until the DMC meeting in phase 2, the Sponsor will share with the DMC all SAEs occurring during the trial, and an unplanned DMC meeting can be held at the request of either the DMC or the Sponsor safety committee.

During the conduct of phase 2, an additional DMC meeting will be held when the 10th patient across cohorts has completed Cycle 1 to evaluate whether the trial should be modified, stopped, or continue unchanged.

The Sponsor safety committee will evaluate the recommendations provided by the DMC after each DMC meeting. Any significant finding/recommendation from the DMC and endorsed by the Sponsor safety committee will be communicated to the regulatory authorities and IRB/IEC as appropriate, and to the sites.

Responsibilities, procedures, content of the DMC packages, and workflow of the DMC are specified in the DMC charter.

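### The DLT-evaluable analysis set requires 4 administrations in a period that the synopsis and section 6.2.3 say covers up to 3

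*Combined protocol and SAP*

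**What the plan says.** Section 11.3.3 gives two routes into the DAS. A phase 1 patient enters by having a DLT in the evaluation period, or by having sufficient safety evaluations together with "at least 80% of the planned doses on each of the 4 administrations in the DLT evaluation period".

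Section 6.2.3, at the end of the list of exceptions, describes DLT collection over Cycles 1 and 2 (4 weeks) and adds: "This will allow for the evaluation of up to 3 investigational medicinal product (IMP) administrations". The synopsis repeats this: "This will allow for the evaluation of up to 3 IMP administrations".

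The length of the period is stated consistently. Sections 6.1 and 6.2.1.3 give 28 days, the headers of Tables 3-1 and 3-2 give 2 cycles, and section 9.9.3 joins the two by placing DMC review "after completion of the DLT evaluation period (2 treatment cycles/28 days) for the last patient in each dose level".

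Section 11.4.1 bases the evaluation of DLTs on the DAS and uses the DLT information to guide escalation and determine the MTD. Table 6-3 and two of the stopping criteria in section 6.2.1.5 are indexed by the number of DLT-evaluable patients.

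On non-evaluability, section 6.2.1.3 says only this, and section 6.3.5 repeats it: "If patients are withdrawn prematurely without having experienced a DLT, they will be considered non-evaluable and may be replaced".

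**The concern.** The three statements about the number of administrations are all visible and all current, and they describe the same period. A requirement met on each of 4 administrations cannot be satisfied in a period that holds at most 3.

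The DAS supplies the denominator for the DLT rate. A DLT-free patient who is wrongly left out raises the observed rate at that dose level. If the rule excludes all such patients, the rate at any level with a DLT is 100% by construction. A definition that works only when it is not read literally leaves evaluability to case-by-case judgement in an open-label escalation.

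**Working it through.** **Inputs**

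| Item | Value | Source |
|---|---|---|
| Administrations required for a DLT-free patient | 4, each at 80% or more | 11.3.3 |
| Administrations in the period | up to 3 | 6.2.3, synopsis |
| Cycle length | 14 days | 6.2.1.1 |
| DLT evaluation period | 2 cycles, 28 days | 9.9.3, Tables 3-1 and 3-2, 6.1, 6.2.1.3 |
| Target DLT rate | 28% | Appendix 1 |
| p_saf, p_tox | 0.65 × 0.28 = 0.182; 1.4 × 0.28 = 0.392 | Appendix 1 |

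**Step 1. Are the decision rules themselves sound?** With φ = 0.28:

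- λ_e = ln[(1 − p_saf)/(1 − φ)] / ln[φ(1 − p_saf)/(p_saf(1 − φ))] = ln(0.818/0.72) / ln(0.22904/0.13104) = 0.1276/0.5584 = 0.2285. The plan states 0.229.
- λ_d = ln[(1 − φ)/(1 − p_tox)] / ln[p_tox(1 − φ)/(φ(1 − p_tox))] = ln(0.72/0.608) / ln(0.28224/0.17024) = 0.1691/0.5055 = 0.3344. The plan states 0.334.

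From these boundaries the escalate and de-escalate rows of Table 6-3 reproduce for n = 2 to 9. The disallow row reproduces for n = 3 to 9 with a uniform prior and a posterior probability above 0.95 that the DLT rate exceeds 28%. At n = 2 the table gives NA for disallowing. The problem is therefore not in the boundaries but in who is counted.

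**Step 2. Is it the same period?** Yes: 2 × 14 = 28 days. A difference in window length does not explain the two counts.

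**Step 3. The two branches.**

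- *If 4 is right*, section 11.3.3 can be applied as written, and the synopsis and section 6.2.3 understate the count.
- *If 3 is right*, a DLT-free patient has at most 3 administrations in the period and cannot meet the criterion on 4. Only the DLT route into the DAS remains. With k DLTs among n treated patients, the set holds k patients and its DLT rate is k/k.

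**Step 4. What the second branch would do if applied literally.**

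| DLTs / patients | Rate | Table 6-3 | DAS as written | Table 6-3 on that set |
|---|---|---|---|---|
| 0/3 | 0% | escalate | 0/0 | no column |
| 1/6 | 16.7% | escalate | 1/1 | no column (table starts at 2) |
| 2/9 | 22.2% | escalate | 2/2 | de-escalate |
| 3/9 | 33.3% | remain, and stop | 3/3 | disallow |

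When every member of the set has a DLT, Table 6-3 cannot return an escalation for any n from 2 to 9. Two stopping criteria in section 6.2.1.5 also become unreachable. The optional stop needs 6 evaluable patients with at most 1 DLT. The stop at 9 evaluable patients needs a decision to remain, which Table 6-3 gives only at 3 DLTs.

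**The case against.** **Someone would notice.** A rule that removes every DLT-free patient would show itself at the first cohort. Escalation passes through the DMC and the sponsor's safety committee (6.2.1.4, 9.9.3), and the final MTD may differ from the statistical estimate (6.2.1.6). This stands. It is why Step 4 describes the literal rule and does not predict what the trial would do. It does not make the three statements agree.

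**The full protocol may settle the count.** Table 6-1 and the dosing text are not visible. This also stands, but whichever count Table 6-1 supports, at least one visible statement is wrong.

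Three stronger readings are tempting and are not supported.

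- *That 3 is the right number.* The pre-dose antibody samples in Table 3-1, footnote p, are taken "Pre-dose on Day 1 and 8 of Cycle 1, Day 1 of Cycles 2-13, and EOT", and the CYP450 restriction in section 7.2.6 is consistent with a second dose on Day 8. If those were the dosing days, 3 would fall in Days 1 to 28. But sampling days are not a dosing table, so this remains an inference.
- *That the window is defined in two ways and that this produced the two counts.* Footnote k of Tables 3-1 and 3-2 says "DLTs should be reported from the first dose of IMP and the following 28 days", which could be stretched to Day 29. It is an instruction on reporting, however. The places that define the period give 28 days or 2 cycles, and section 9.9.3 equates them. The origin of the two counts is unknown.
- *That a probability of a wrong escalation decision can be attached.* One could drop a single DLT-free patient from Table 6-3 and compute how often the decision changes. Neither branch loses exactly one patient, and a fixed-n binomial ignores how the design reaches each n. Such figures would not measure this defect.

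**Replacement is partly covered.** A DLT-free patient below 80% on a required administration is outside the DAS under section 11.3.3, and a dose delay of more than 21 days for toxicity is itself a DLT in section 6.2.3. What remains open is whether a patient who stays in the trial but misses the dosing criterion may be replaced, and how shorter delays count.

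**Conclusion.** The definition of the DAS is wrong as written in at least one place, and it should be fixed. Confidence in the contradiction is high, because it rests on three explicit statements and needs no inference about the schedule.

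The size is all or nothing. If the true count is 4, the DAS is unaffected and the error lies in the synopsis and section 6.2.3. If it is 3, no DLT-free patient qualifies under the literal text. The documents give no basis for a figure between these, and review by the DMC and the sponsor makes literal application unlikely.

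A reader might infer that the escalation or the MTD is unsound. The documents do not support that: the boundaries and Table 6-3 reproduce, and the decisions are reviewed. What is missing is a usable definition of the set on which section 11.4.1 bases the DLT evaluation.

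**What to change.** 1. In section 11.3.3, replace the fixed number by a reference to each administration scheduled in the DLT evaluation period, keeping the 80% criterion.
2. Reconcile the number of administrations across section 11.3.3, section 6.2.3, the synopsis and Table 6-1. This review does not presume which count is right.
3. As minor clarifications, align footnote k of Tables 3-1 and 3-2 with the period in section 9.9.3. Align sections 6.2.1.3 and 6.3.5 with the DAS by stating whether a DLT-free patient who remains in the trial but does not meet the dosing criterion may be replaced. State also how an administration delayed within the 3 weeks accepted in section 7.1.2.3 counts towards evaluability, since item 1 alone does not settle that.

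The cost is one sentence in section 11.3.3, one consistent count, a short edit to footnote k and one or two clarifying sentences, all carried into the SAP definition of the DAS. No patients, visits or procedures are added.

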#### 11.3.4 PK Analysis Set

The PK analysis set (PKAS) consists of all patients who receive at least 1 dose of nivatrotamab and have at least 1 evaluable concentration measurement of nivatrotamab. Patients will be removed from the estimation of certain PK parameters on an individual basis due to, for example, missing PK samples or inadequate dosing such that the PK parameters cannot be appropriately derived or summarized. These patients will be identified at the time of the analyses along with the reason for their removal.

## 11.4 Statistical Analysis

### 11.4.1 Dose-limiting Toxicities

DLTs observed during the DLT evaluation period will be listed and summarized in a table by Medical Dictionary for Regulatory Activities (MedDRA) system organ class (SOC) and preferred term (PT). The information from the DLTs will be used to guide the escalation and de-escalation rules as per the mBOIN-design and ultimately determine the MTD. The evaluation of DLTs will be based on the DAS.

Patients with and without DLTs will be plotted in a graph with dose level on the vertical axis and patient number on the horizontal axis.

### 11.4.2 Maximum Tolerated Dose

Upon completion of the mBOIN-design, the MTD is preliminarily estimated as the dose for which the isotonic estimate of the DLT rate is closest to the target toxicity level. If there are ties, either the highest dose level when the estimate of the DLT rate is smaller than the target or the lowest dose level when the estimate of the DLT rate is greater than the target, will be selected from the ties.

This MTD will be estimated using the `select.mtd()`-function in the `BOIN`-package for the R software (R software package ‘`BOIN`’ v 2.7.0 or later ).

